9.2 Adverse Event and Reporting Definitions

An adverse event or adverse experience is any untoward medical occurrence in a clinical investigation patient who is administered a medicinal product. An adverse event can be any unfavorable and unintended sign, symptom, or disease temporally associated with the use of a medicinal product, whether or not considered related to the medicinal product. Pre-existing conditions that increase in frequency or severity or change in nature during or as a consequence of use of a drug are also considered as adverse events. Adverse events may also include pre- or post-treatment complications that occur as a result of protocol-mandated procedures (eg, invasive procedures such as biopsies).

An AE does not include:

- Medical or surgical procedures (eg, surgery, endoscopy, tooth extraction, transfusion). The condition that leads to the procedure is the adverse event

- Situations where an untoward medical occurrence has not occurred (eg, hospitalization for elective surgery, social and/or convenience admissions)

- Overdose of either study drug or concomitant medication without any signs or symptoms unless the patient is hospitalized for observation.

The relationship to study drug therapy should be assessed using the following definitions:

Not Related: Evidence exists that the AE has an etiology other than the study drug (eg, pre-existing condition, underlying disease, intercurrent illness, or concomitant medication).

Possibly/Probably Related: A temporal relationship exists between the event onset and administration of the study drug. It cannot be readily explained by the patient's clinical state, intercurrent illness or concomitant therapies. In case of cessation or reduction of the dose, the event abates or resolves and reappears upon rechallenge. It should be emphasized that ineffective treatment should not be considered as causally related in the context of AE reporting.

A serious adverse event is defined as any adverse drug experience occurring at any dose that results in any of the following outcomes:

- Death
- Life-threatening situation (patient is at immediate risk of death)

- -Inpatient hospitalization or prolongation of existing hospitalization (excluding those for study therapy, disease-related procedures, palliative or hospice care, or placement of an indwelling catheter, unless associated with other serious events)
- Persistent or significant disability/incapacity
- Congenital anomaly/birth defect in the offspring of a patient who received study drug
- Other: Important medical events that may not result in death, be immediately life-threatening, or require hospitalization, may be considered an SAE when, based upon appropriate medical judgment, they may jeopardize the patient or may require medical or surgical intervention to prevent one of the outcomes listed in this definition. Examples of such events are:

Intensive treatment in an emergency room or at home for allergic bronchospasm Blood dyscrasias or convulsions that do not result in hospitalization Development of drug dependency or drug abuse

9.3 **Reporting of Serious Adverse Events**

All Serious Adverse Events will be reported to the University of Texas M.D. Anderson Cancer Center IRB within five working days of knowledge of the event.

.Serious Adverse Events will also be reported to Merck, Sharp and Dohme, Corp.,. (Attn: Worldwide Product Safety; [contact]) with copies of all serious and/or unexpected adverse experiences, within two working days. Investigator will establish and maintain records and make reports to the IRB with copies, as described above, to Merck for the following Adverse Experiences: (1) all serious, unexpected, adverse events, (2) any significant increase in the frequency of serious expected adverse events, and (3) any significant increase in the frequency of therapeutic failures. Additionally, Investigator will report any pregnancy occurring in association with use of a Merck Product to Merck, Sharp and Dohme, Corp.,. (Attn: Worldwide Product Safety; [contact]). For any serious thromboembolic Adverse Experiences, investigator will fax, at the same time as the submission to Merck of the original report, the additional information set forth on the attached questionnaire (Appendix L) In addition, if any new information becomes available regarding any Adverse Experience, that new information will be submitted to Worldwide Product Safety within two working days.

10.0 CRITERIA FOR DISCONTINUATION OF TREATMENT

- 1. Progressive disease as defined above after one cycle of treatment. (Section 8.2.5).
- 2. The development of unacceptable toxicity.
- 3. Patient refusal.
- 4. Non-compliance or inability to comply with protocol requirements by patient
- 5. Treatment related adverse events not resolved within a 4 weeks rest period or requiring more than two dose de-escalations of any drug whichever is earlier.

Patients may remain on treatment as long as disease progression is not observed and the patient is not experiencing unacceptable toxicity (see 8.9). Although therapy is planned for one year, the patient may remain on treatment beyond this time if both the patient and physician agree that further therapy is in the patient's best interests.

11.0 STATISTICAL CONSIDERATIONS

11.1 Phase I component

The phase I component will be a non randomized trial in which Arm 1 and Arm 2 will be opened simultaneously with consecutive patients enrolled alternately to each arm, and sequentially to each dose level. If the MTD is reached earlier in one arm, all subsequent patients will be enrolled to the other arm. Once the MTD for Arm 1 and Arm 2 is known, Arm 3 will begin accrual. A maximum of 54 patients will be enrolled in this component of the trial. The MTDs obtained in the Phase I component will be used as the Phase II dose in the next component of the trial.

11.1.1. Arm 1 of the phase I component was to assess the MTD of vorinostat in combination with a fixed dosage of cRA as shown in the table below. As noted above in section 5.1.1, the MTD of vorinostat in combination with cRA has been established in the current trial.

Level	Arm 1				
	Vorinostat cRA				
	(mg/day x 14 days) ((mg/m2/day x 21 days)				
0 (starting dose)	300	100			
1	400	100			
II	500	100			

11.1.2. Arm 2 of the phase I component was aimed at assessing the MTD of Carboplatin (CBT) in combination with a fixed dosage of cRA. With the change in the combination to temozolomide with isotretinoin, the MTD is already known; hence, a phase I trial of this arm will not be needed.

11.1.3. Arm 3 of the phase I component will assess the MTD vorinostat in combination with fixed doses of temozolomide + cRA. For temozolomide, the Phase II dose determined in Arm 2 will be used. The enrollment will proceed as outlined for Arm 1 (cohorts of 3 patients enrolled to each dose level), declaring MTD for Temozolomide in combination with vorinostat and cRA once DLT is noted.

Level	Arm 3		
	Vorinostat (mg/day x days 1-7 and 15-21)	cRA (mg/m2/day x 21 days)	Temozolomide (mg/m2/day on days 1-7 &15-21
-111	300	100	100
-11	300	100	125
-I	400	100	125
0 (starting dose)	400	100	150
I	500	100	150

- If the initial cohort of patients at starting dose level 0 do not experience DLT, the next cohort of patients will be treated by dose escalation to level I (with increase in the dose of vorinostat). If no patients experience DLT in this cohort, 3 more patients will be enrolled to expand this cohort to a total of 6 patient to confirm that MTD has been achieved. If no DLT is noted or if only 1/6 patients experience DLT after this expansion of level I, this dose level will be declared the MTD and hence the phase II dose.
- If 2/6 patients have DLT after expansion of dose level I, dose level 0 will be declared as the MTD and hence the phase II dose.
- If Dose level 0 exceeds the MTD, lower doses will be studied as noted in the table above. If 1/3 patients have DLT at any dose level, the cohort will be expanded by 3 more patients. If ≥2/6 patients experience DLT, the MTD will be considered as being exceeded and the dose will be de-escalated to the next lower dose level and 3 new patients will be enrolled at that level. If none or only 1/6 patients experience DLT after dose de-escalation to the lower level, this dose level will be declared as the MTD, and will be utilized for the phase II component of the study.

11.2 Phase II component

This is an adaptive randomized phase II trial to compare three treatment arms: a) vorinostat + Isotretinoin, b) Temozolomide + Isotretinoin, and c) vorinostat + Isotretinoin + Temozolomide, in patients with recurrent GBM. The primary outcome is Progression Free Survival (PFS). Patients will be randomized among arms using a Bayesian adaptive algorithm. Technical details of this methodology are given in Appendix H. Patients will be randomized fairly among the three arms at the start of the trial (for the first 30 patients). Thereafter, as the trial progresses and data accrue, the randomization will become unbalanced in favor of the

treatment that, on average, has better results in terms of failure time. Therefore, each successive patient is more likely to receive the treatment with better results, on average. A minimum of 30 and a maximum of 135 patients will be accrued and there will be 6 months follow up after the last patient is accrued. Based on an anticipated accrual rate between 3 and 5 patients per month, the maximum trial accrual period will be between 45 and 27 months.

Patients enrolled in the surgical arm of the phase II component will be randomized to one of the three treatment arms after surgery is performed. In surgical patients, cycle 1 will be the first cycle of treatment after surgery. PFS in these patients will be determined from the date of randomization into the chemotherapy arms (i.e. after surgery for tumor resection), and not from the date of registration in the trial.

The tables given below summarize operating characteristics of the design. The historical median PFS is 3 months. The tables below assume an accrual rate of either 3 or 5 patients per month. The trial will be stopped early and a treatment selected as being "better" if the probability that one treatment's median PFS is larger than the other's PFS exceeds 0.975. If the trial does not stop early and the maximum 135 patients are accrued, a treatment is selected as being "better" if the probability that one treatment's median PFS is larger than the other's PFS exceeds 0.85. A treatment arm will be dropped at any point during the trial if the probability that the treatment's median PFS is larger than 3 months is less than 0.01. The "# of patients treated" row is the average number of patients treated on a given arm under the given scenario. When the medians all equal to 3 months (scenario 1), the probability of selecting one of the three arms (i.e., a false positive result) is at most 6% for both accrual rates. The probability of selecting the best treatment (i.e., a true positive result) for scenario 4, when the medians PFS are 3, 3, and 7 months for the arms, respectively, is 99.5% for the accrual rate of 3 patients per month and 99.7% for the accrual rate of 5 patients per month.

At each evaluation when a new patient is coming in the study, the data for patients who have been followed till that time and not yet progressed are accounted in the analysis.

The trial will be conducted using a website developed in the Department of Biostatistics at MD Anderson Cancer Center. Through the web interface, the users have the ability to randomize patients, update last evaluation date and current patient status. When a patient is randomized the calculations are based on all available data entered into the website. The results of the randomization are displayed to the screen for the user to view. All data is stored in a secure SQL server database.

Run Date: Wed May-05-2010 03:46:39 PM Trial Design

Primary endpoint	Time-To-Event
Number of arms	3

2006-0709 March 4, 2011 Page 48 of 57

Minimum patient accrual	30
Maximum patient accrual	135
Number of patients to randomize fairly	30
Minimum randomization probability	0.1
Tuning parameter	1
Additional follow-up	6
Goal of study	Maximize θ

Prior Parameters

Arm Name	Description	Prior Parameters (a, b)
Arm1	V+A	(2.009, 3.027)
Arm2	T+A	(2.009, 3.027)
Arm3	V+A+T	(2.009, 3.027)

Stopping Rules

Suspend accrual to an arm if $Pr(\theta_i > max(\theta_{j \neq i}) | Data) < P_L$ Stop the trial and select an arm as superior if $Pr(\theta_i > max(\theta_{j \neq i}) | Data) > P_U$ At the final analysis select an arm as superior if $Pr(\theta_i > max(\theta_{j \neq i}) | Data) > P_U^*$ Suspend accrual to an arm if $Pr(\theta_i > \theta_{min}) | Data) < P_L^*$

Stopping Rule Details

Arm	Group	PL	Ρυ	P∪*	θ min	Pl*
Arm1	No groups	0.01	0.975	0.85	3	0.01
Arm2	No groups	0.01	0.975	0.85	3	0.01
Arm3	No groups	0.01	0.975	0.85	3	0.01

SIMULATION PARAMETERS WITH ACCRUAL OF 3 PATIENTS/MONTH

Number of patients accrued each month	3
Number of repetitions	1000
Random number generator seed	123456789

Scenario 1						
Average	Trial Length	49.5 months				
Arm	True Median Survival	Pr(Selected)	Pr(Selected Early)	Pr(Stopped Early)	# Patients (2.5%,97.5%)	
V+A	3	0.054	0.015	0.082	43.7 (11,88)	

2006-0709 March 4, 2011 Page 49 of 57

T+A	3	0.051	0.013	0.081	43.8 (11,90)
V+A+T	3	0.061	0.015	0.083	43.8 (11,89)
	·			-	-
Scenario 2	2				
Average	Trial Length	43.3 months			
Arm	True Median Survival	Pr(Selected)	Pr(Selected Early)	Pr(Stopped Early)	# Patients (2.5%,97.5%)
V+A	3	0.002	0.002	0.566	20.8 (10, 49)
T+A	4	0.038	0.018	0.301	36.7 (10, 89)
V+A+T	5	0.54	0.261	0.026	59.4 (10, 98)
	-				
Scenario 3	3				
Average	Trial Length	37.5 months			
Arm	True Median Survival	Pr(Selected)	Pr(Selected Early)	Pr(Stopped Early)	# Patients (2.5%,97.5%)
V+A	3	0	0	0.918	143(10.28)
$T+\Delta$	5	0 019	0 015	0.510	31.9 (10, 86)
$V + \Delta + T$	7	0.758	0.015	0.020	57.6 (10, 101)
VIAII	/	0.750	0.400	0.015	57.0 (10, 101)
Scenario	1				
Scenario -	*				
Average	Trial Length	21.9 months			
Arm	True Median	Pr(Selected)	Pr(Selected Early)	Pr(Stopped Early)	# Patients (2.5%,97.5%)
1/1.0	Survivai				144(10.22)
V+A	3	0	0	0.98	14.4 (10, 32)
I+A	3	0	0	0.979	14.3 (10, 32)
V+A+I	/	0.995	0.949	0	36 (10,90)
~ •	_				
Scenario :	5				
Average	Trial Length	28.6 months			
Arm	True Median Survival	Pr(Selected)	Pr(Selected Early)	Pr(Stopped Early)	# Patients (2.5%,97.5%)
V+A	3	0	0	0.935	14.3 (10, 28)
T+A	4	0.005	0.005	0.833	20.8 (10, 56)
$V + \Delta + T$	7	0.96	0.803	0.005	475(10.97)
,					
Scenario (6				
Average	Trial Length	10.3 months			
Arm		Pr(Selected)	Pr(Selected	Pr(Stopped	# Datiente
AIIII	nue	FIL Selected)	In Selected	Tert Stopped	

2006-0709 March 4, 2011 Page 50 of 57

	Median Survival		Early)	Early)	(2.5%,97.5%)
V+A	1	0.025	0.001	0.819	10.2 (10,13)
T+A	1	0.015	0	0.802	10.3 (10,13)
V+A+T	1	0.012	0	0.806	10.3 (10, 13)

Run Date: Wed May-05-2010 03:57:33 PM

Trial Design

Primary endpoint	Time-To-Event
Number of arms	3
Minimum patient accrual	30
Maximum patient accrual	135
Number of patients to randomize fairly	30
Minimum randomization probability	0.1
Tuning parameter	1
Additional follow-up	6
Goal of study	Maximize θ

Prior Parameters

Arm Name	Description	Prior Parameters (a, b)
Arm1	V+A	(2.009, 3.027)
Arm2	T+A	(2.009, 3.027)
Arm3	V+A+T	(2.009, 3.027)

Stopping Rules

Suspend accrual to an arm if $Pr(\theta_i > max(\theta_{j\neq i}) | Data) < P_L$ Stop the trial and select an arm as superior if $Pr(\theta_i > max(\theta_{j\neq i}) | Data) > P_U$ At the final analysis select an arm as superior if $Pr(\theta_i > max(\theta_{j\neq i}) | Data) > P_U^*$ Suspend accrual to an arm if $Pr(\theta_i > \theta_{min}) | Data) < P_L^*$

Stopping Rule Details

Arm	Group	PL	Ρυ	Ρ υ*	θ_{min}	P∟*
Arm1	No groups	0.01	0.975	0.85	3	0.01
Arm2	No groups	0.01	0.975	0.85	3	0.01
Arm3	No groups	0.01	0.975	0.85	3	0.01

SIMULATION PARAMETERS WITH ACCRUAL OF 5 PATIENTS/MONTH

Number of patients accrued each month	5
Number of repetitions	1000

2006-0709 March 4, 2011 Page 51 of 57

Random number generator seed

123456789

Scenario 1					
Average	Trial Length	31.8 months			
Arm	True Median Survival	Pr(Selected)	Pr(Selected Early)	Pr(Stopped Early)	# Patients (2.5%,97.5%)
V+A	3	0.04	0.014	0.076	43.8 (11,90)
T+A	3	0.046	0.02	0.08	43.7 (11, 86)
V+A+T	3	0.055	0.018	0.073	43.5 (10,88)
Scenario 2					
Average	Trial Length	28.9 months			
Arm	True Median Survival	Pr(Selected)	Pr(Selected Early)	Pr(Stopped Early)	# Patients (2.5%,97.5%)
V+A	3	0.001	0.001	0.564	21.8 (10,49)
T+A	4	0.042	0.021	0.253	38.8 (10, 87)
V+A+T	5	0.492	0.207	0.023	61.1 (14, 96)
Scenario 3	;				
Average	Trial Length	25.1 months			
Arm	True Median Survival	Pr(Selected)	Pr(Selected Early)	Pr(Stopped Early)	# Patients (2.5%,97.5%)
V+A	3	0	0	0.915	15.5 (10,33)
T+A	5	0.014	0.012	0.493	33.5 (10, 83)
V+A+T	7	0.745	0.444	0.012	60.4 (13,99)
Scenario 4	ļ				
Average	Trial Length	15.3 months			
Arm	True Median Survival	Pr(Selected)	Pr(Selected Early)	Pr(Stopped Early)	# Patients (2.5%,97.5%)
V+A	3	0.001	0.001	0.968	16 (10, 33)
T+A	3	0	0	0.973	15.8 (10, 33)
V+A+T	7	0.997	0.931	0.001	42.4 (10,91)
Scenario 5					
Average Trial Length 20.2 months					
Arm	True	Pr(Selected)	Pr(Selected	Pr(Stopped	# Patients

2006-0709 March 4, 2011 Page 52 of 57

	Median Survival		Early)	Early)	(2.5%,97.5%)
V+A	3	0	0	0.944	15.8 (10, 32)
T+A	4	0.003	0.003	0.803	23.7 (10,64)
V+A+T	7	0.949	0.727	0.003	53.2 (11,98)

Scenario 6

Average Trial Length 6.28 months

Arm	True Median Survival	Pr(Selected)	Pr(Selected Early)	Pr(Stopped Early)	# Patients (2.5%,97.5%)
V+A	1	0.02	0	0.768	10.4 (10,14)
T+A	1	0.022	0	0.762	10.5 (10,14)
V+A+T	1	0.024	0	0.757	10.5 (10, 15)

(Abbreviations: PFS: Progression free survival; V, vorinostat; A, accutane (isotretinoin); T, temozolomide)

Patients' demographic information at baseline will be analyzed, with data summarized in tables listing the number of subjects per treatment group in order to assess comparability. The Student t-test or the Wilcoxon rank sum test will be used to compare continuous variables between two different patient groups. The chi-squared test or the Fisher exact test will be applied to assess the association between two categorical variables.

Time-to-event outcomes, including progression-free survival and overall survival, will be estimated using Kaplan-Meier method. The log-rank test will be performed to test the difference in time-to-event distributions between patient groups. Cox proportional hazards model will be utilized to include multiple covariates in the time-to-event analysis.

Toxicity data will be summarized by frequency tables. The association between the types and severity of toxicity and the treatment groups will be evaluated. No formal statistical testing will be performed on these summary data.

To provide formal safety monitoring in the Phase II portion of the trial, after enrollment of every 10 patients into each of the three arms, we will assess the group for toxicity. If dose limiting toxicity as defined in the phase I portion of the trial is reached =/> 1/3 of patients despite dose reduction, the arm will stop accrual. If dose reduction permits continuation of treatment in these patients, the starting dose levels for the remainder of the patients on the trial will be modified to a lower starting dose (-1) level specified in the dose modification section.

For the efficacy endpoint, intent-to-treat analysis will be applied to the randomized and eligible patients. For the toxicity endpoint, as-treated analysis

will be used to include any patient who received the treatment – regardless of the eligibility nor the duration or dose of the treatment received.

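### Section 11.2: the written selection rule and the printed simulation tables follow different decision rules, as scenario 6 shows

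*Combined protocol and SAP*

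**What the plan says.** The narrative of section 11.2 gives two routes to selection. Early: "The trial will be stopped early and a treatment selected as being" better if the posterior probability that its median PFS is the larger exceeds 0.975. Late: "If the trial does not stop early and the maximum 135 patients are accrued, a treatment is selected as being" better if that probability exceeds 0.85. There is one rule for closing an arm: "A treatment arm will be dropped at any point during the trial if the probability" that its median PFS exceeds 3 months is below 0.01. On size and follow-up: "A minimum of 30 and a maximum of 135 patients will be accrued and there will be 6 months follow up" after the last patient.

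The program output printed in the same section words two things differently.
- The late rule reads "At the final analysis select an arm as superior if" the probability exceeds P_U*, with no mention of 135 patients.
- It lists a further rule: accrual to an arm is suspended if the probability that it is the best arm falls below P_L.

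The thresholds (P_L, P_U, P_U*, θmin, P_L*) are the same for each arm, for example "Arm1 No groups 0.01 0.975 0.85 3 0.01".

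**The concern.** The operating characteristics are the evidence that the decision rules behave acceptably, so they must come from the rules in the text. Scenario 6 appears to show arms selected by the late rule with about 31 patients in total, where the text requires 135.

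The trial is to be run through a website that does the calculations. If the website follows the simulated rules, an arm with about 10 patients and no further follow-up could be declared better at 0.85. If it follows the text, the printed tables do not fully describe the trial.

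**Working it through.** **Inputs (section 11.2, scenario 6, all medians 1 month, 1,000 repetitions)**

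| | 3/month | 5/month |
|---|---|---|
| Pr(Selected), three arms | 0.025 + 0.015 + 0.012 = 0.052 | 0.020 + 0.022 + 0.024 = 0.066 |
| Pr(Selected Early), three arms | 0.001 | 0 |
| Selected, not early | 0.051 | 0.066 |
| Mean total N | 10.2 + 10.3 + 10.3 = 30.8 | 10.4 + 10.5 + 10.5 = 31.4 |
| Average trial length | 10.3 months | 6.28 months |

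**Step 1. How many trials can have reached 135?** Every trial has at least 30 patients. If a share p reaches 135, mean N ≥ 30(1 − p) + 135p, so p ≤ (mean N − 30)/105.
- 3/month: 0.8/105 = 0.8%. With each arm mean at its rounding limit, 0.95/105 = 0.9%.
- 5/month: 1.4/105 = 1.3%. At the rounding limit, 1.55/105 = 1.5%.

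Had all the non-early selections occurred at 135, mean N would be at least 0.051 × 135 + 0.949 × 30 = 35.4 and 0.066 × 135 + 0.934 × 30 = 36.9. In counts, at least 51 − 9 = 42 and 66 − 14 = 52 of the 1,000 trials selected non-early below 135 patients. This needs no model.

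**Step 2. Was follow-up applied?** Accrual time alone is 30.8/3 = 10.27 and 31.4/5 = 6.28 months, which equal the stated lengths. In scenario 1 at 3/month, accrual is (43.7 + 43.8 + 43.8)/3 = 43.8 months against 49.5 stated, so follow-up was applied there.

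**Step 3. Which rule produces the tables?** The design was simulated with 1,000 to 4,000 runs per variant. Assumptions: exponential PFS, an inverse-gamma (2.009, 3.027) prior on the median (mean 3.027/1.009 = 3.0 months), 30 patients randomized equally, then allocation in proportion to the probability of being best with a 0.1 floor, and a look at each new patient.

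| Rule (3/month; 5/month) | Selected, not early | Mean N | Length, months | Stopped early, per arm |
|---|---|---|---|---|
| Printed tables | 0.051; 0.066 | 30.8; 31.4 | 10.3; 6.28 | 0.80–0.82; 0.76–0.77 |
| End when at most one arm is open, 0.85 at once | 0.055; 0.066 | 30.6; 31.1–31.2 | 10.2; 6.2 | about 0.81; 0.77 |
| Same, 0.85 after 6 more months | 0.052; 0.054 | 30.6; 31.1 | 16.2; 12.2 | about 0.81; 0.77 |
| End when all three are suspended, 0.85 at once | about 0.02 | about 33; 35 | 11.0; 6.9–7.0 | about 0.998 |

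Only the first simulated variant fits every column. With the text's rules taken literally, any-arm selection is about 0.003 (N 32.8) at 3/month and 0.006 (N 34.5) at 5/month, all of it early, and no run reached 135.

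**Step 4. Was the P_L rule active?** Scenario 2 at 3/month tabulates stopping of 0.566, 0.301 and 0.026. Simulation gives 0.575, 0.311 and 0.028 with P_L, and 0.305, 0.267 and 0.020 without it. This counts an arm as stopped if it was suspended or lost to an early winner, a convention the supplied text does not define.

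**Step 5. Do the quoted figures move?** Without P_L, scenario 4 best-arm selection is 0.992 and 0.995, against 0.995 and 0.997 printed. Scenario 1 selection summed over arms is about 0.15 to 0.18, against 0.166 and 0.141 in the tables. In scenario 1 at 3/month only about 0.4% of runs selected non-early below 135 patients; in scenario 4 none did.

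**The case against.** The strongest reply is that text and output share every main setting: 30 patients randomized equally, a maximum of 135, thresholds of 0.975, 0.85 and 0.01, a 3-month benchmark and 6 months of follow-up. The output is itself part of section 11.2, and its final analysis is not tied to 135 patients. On this view one case has gone unwritten. That stands in part. A reader might infer that the tables come from a wholly different design, and the shared settings do not support that. But the text does tie 0.85 to 135 patients, and the tables contradict it.

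Technical details are said to be in Appendix H, which is not in the supplied text. The last-arm rule may be there, so the supportable statement is that section 11.2 does not give it.

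A reader might also infer that the error rates quoted in the text are wrong. Those are for scenarios 1 and 4, and step 5 shows they are little affected.

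Nor would a selection in scenario 6 send a poor regimen straight to a larger trial. Section 2.8 also requires a favourable comparison with historical controls, and selection with about 10 patients per arm is already possible under the written 0.975 rule.

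Finally, the text says "A treatment arm will be dropped at any point during the trial" while the output speaks of suspending accrual. A reader might conclude that simulated arms could reopen. The stopping columns cannot settle this, because the supplied text does not define them, and scenario 6 comes out almost the same either way. The wording conflict is real; reopening is only an inference.

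**Conclusion.** The point holds. The written selection rule and the printed operating characteristics cannot both describe the trial. In scenario 6 the tables show non-early selection in 5.1% and 6.6% of trials, where at most about 0.9% and 1.5% can have met the 135-patient condition, and no 6-month follow-up was applied. Under the written rule, selection there would be about 1% or less.

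The contradiction rests on table arithmetic, the 30-patient minimum, and reading non-early as selected minus selected early. The tables do not label the threshold behind each selection, but 0.85 is the only non-early rule listed.

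That the program ended the trial with at most one arm open and applied 0.85 at once is the best-fitting explanation among the variants tried. It depends on the assumed exponential and inverse-gamma model. Placing the prior on the mean instead gave a scenario 6 N of about 45 and did not fit.

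The P_L rule's absence from the text is a matter of record. The practical effect is concentrated where all arms are poor.

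**What to change.** In section 11.2:
1. State what happens when fewer than two arms remain open before 135 patients, and which threshold and follow-up then apply. Keeping the written rule means selection only above 0.975 before 135 patients plus 6 months of follow-up, and otherwise no selection.
2. State the P_L rule in the text, or remove it from the program.
3. Say whether suspension of an arm is permanent, and use one term for it.
4. Define the stopped-early column.

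Then confirm that the website runs exactly these rules, and re-run and replace both sets of tables.

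The cost is wording, a website check and a simulation re-run. No patients are added. Some table figures will change, chiefly in scenario 6, and the arm-stopping columns will change if P_L is removed.

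### The stated false-positive ceiling of 6% is a single-arm figure; the protocol's own tables give about 17% and 14% for selecting any arm under the null

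*Combined protocol and SAP*

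**What the plan says.** Section 11.2 (Phase II component) describes scenario 1, in which every arm has a true median PFS of 3 months, and states that "the probability of selecting one of the three arms (i.e., a false positive result) is at most 6% for both accrual rates". It then quotes the chance of picking the best arm in scenario 4, 99.5% and 99.7% at the two accrual rates.

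The stopping rules in the same section define selection through the posterior probability that an arm's median exceeds the larger of the other two. The early threshold P_U is 0.975, at which the trial stops. The last look uses P_U* = 0.85: "At the final analysis select an arm as superior if" that same probability exceeds P_U*.

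The scenario 1 tables give Pr(Selected) separately for each arm, from 1000 repetitions at each accrual rate. The largest entry is in the three-drug row at 3 patients per month, "V+A+T 3 0.061 0.015 0.083 43.8 (11,89", where 0.061 is Pr(Selected). No table or sentence gives a trial-wise total.

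**The concern.** The sentence defines the false positive as selection of one of the three arms when none is better. That is a trial-wise event: the trial names a superior regimen, whichever it is. The 6% looks like the largest per-arm entry, reported as if it were the probability of this event.

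It matters because this is the only false-positive rate given in words, and it sits next to the true-positive figures, so the two will be read together. Section 2.8 says the selected regimen is to be considered for a larger trial if it also compares favourably with historical controls. Anyone weighing a declared winner against a 6% error rate would trust it too much.

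**Working it through.** **Inputs** (section 11.2, scenario 1 tables, Pr(Selected) and Pr(Selected Early)):

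| Arm | Selected, 3/month | Early, 3/month | Selected, 5/month | Early, 5/month |
|---|---|---|---|---|
| V+A | 0.054 | 0.015 | 0.040 | 0.014 |
| T+A | 0.051 | 0.013 | 0.046 | 0.020 |
| V+A+T | 0.061 | 0.015 | 0.055 | 0.018 |

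**Source of the stated figure.** The largest single-arm values are 0.061 and 0.055. To the nearest percent the greater of these is 6%, so the stated ceiling is reproduced only as a maximum over arms.

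**Why the arms add.** Let p_i be the posterior probability that arm i has the largest median. Then p_1 + p_2 + p_3 = 1, so two arms cannot both exceed 0.85, still less 0.975. An early selection also ends the trial. Selections of different arms are therefore mutually exclusive, and

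Pr(any arm selected) = sum of the three Pr(Selected) values.

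- 3 per month: 0.054 + 0.051 + 0.061 = **0.166**
- 5 per month: 0.040 + 0.046 + 0.055 = **0.141**

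**Simulation error.** With 1000 repetitions, SE = sqrt(p(1 − p)/1000).

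- 3 per month: sqrt(0.166 × 0.834/1000) = 0.0118, 95% interval 14.3% to 18.9%
- 5 per month: sqrt(0.141 × 0.859/1000) = 0.0110, 95% interval 11.9% to 16.3%

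Neither interval comes near 6%.

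**Ratio to the stated ceiling.** 0.166/0.06 = 2.8 and 0.141/0.06 = 2.35.

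**Could another definition give 6%?**

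- Early selection only: 0.015 + 0.013 + 0.015 = 0.043 and 0.014 + 0.020 + 0.018 = 0.052. Both are below 6%, but the sentence is not limited to early stopping. Most false selections come at the final look: 0.166 − 0.043 = 0.123 and 0.141 − 0.052 = 0.089.
- Treating the arms as independent, 1 − product of (1 − Pr(Selected)): 15.7% and 13.5%.

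**Effect on interpretation.** In scenario 2 (medians 3, 4 and 5 months) the best arm is selected with probability 0.54 at 3 per month and 0.492 at 5 per month. Set against 6%, these are 9.0 and 8.2 times the chance of a false selection under the null. Set against the table totals, they are 0.54/0.166 = 3.3 and 0.492/0.141 = 3.5 times.

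**Rough cross-check.** The design was re-simulated with exponential PFS, an inverse-gamma (2.009, 3.027) prior on each median (mean 3.027/1.009 = 3.0 months), 30 patients randomized equally, a randomization floor of 0.1 and the tabled thresholds. With 1000 runs, any-arm selection was 14.7% at 3 per month if suspended arms may reopen, 17.1% if suspension is permanent, and 15.4% at 5 per month. A second, separately coded version with 800 runs gave 17.4% and 16.9%. The technical details are in Appendix H, which is not in the supplied text, so these are approximate. The 16.9% lies just above the 11.9% to 16.3% interval for the tabled value, although the difference of 2.8 points is only about 1.6 standard errors. The finding rests on the table sums, not on these runs.

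**The case against.** The best defence is that this is a labelling slip. A ceiling worded as a maximum fits a maximum over the per-arm entries, and the phrase about one of the three arms could loosely mean any given arm. On that reading 6% is correct to the nearest percent. The excess of 0.061 over 0.06 is rounding and well within simulation error (SE about 0.008), so nothing should be made of it. All six per-arm values are printed beneath the sentence, so nothing is hidden and a reader can add them.

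Two further points are fair. The documents set no overall type I error target, so no stated requirement is breached. Selection is also not the whole decision to proceed, since section 2.8 adds a comparison with historical controls.

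The table values and the design therefore stand as they are. The sentence does not. It calls the event a false positive result, and a wrongly declared winner is one whichever arm it is. The historical-control step has no numerical criterion, so it cannot be credited with bringing the rate down to 6%. The prose in section 11.2 states the selection rule more loosely, as one treatment's median exceeding the other's, but the tables list the three-way rule among their settings, and under it the sums are exact.

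**Conclusion.** The concern holds. By the protocol's own simulations, the probability of naming a superior arm when all medians are 3 months is 16.6% at 3 patients per month and 14.1% at 5 per month, against a stated ceiling of 6%. That is about one null trial in 6 or 7, rather than one in 17.

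The conclusion assumes only that the tabled Pr(Selected) values were produced under the selection rule printed with them. The totals are estimates from 1000 repetitions, with the intervals given above. This is a misreported operating characteristic of the primary comparison. It does not show that the randomization algorithm or the thresholds are faulty.

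**What to change.** Replace the sentence in section 11.2 with wording such as: *In scenario 1, where every arm has a true median PFS of 3 months, the simulated probability that the trial names a superior arm is 16.6% at 3 patients per month and 14.1% at 5 per month (1000 repetitions each); the largest value for a single arm is 6.1% and 5.5%, respectively.* Adding an any-arm total to each scenario table would prevent the same misreading elsewhere.

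The cost is one corrected sentence and a less favourable stated error rate. Thresholds, sample size and conduct stay as they are. Only if the sponsor actually wants about 6% for the whole trial, which the documents do not say, would P_U and P_U* need re-tuning and every scenario re-running. Stricter thresholds would then be expected to lower the true-positive figures as well.
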